1.6. Compliance

This study will be conducted in compliance with this protocol, Good Clinical Practices (GCP), and all applicable regulatory requirements.

2. OBJECTIVES

The primary objective of this study is:

- To evaluate the efficacy of filgotinib as compared to placebo in establishing combined fistula response at Week 24

The secondary objectives of this study are:

- To evaluate the efficacy of filgotinib as compared to placebo in establishing combined fistula remission at Week 24
- To assess the time to clinical fistula response
- To assess the time to clinical fistula remission
- To evaluate the efficacy of filgotinib as compared to placebo in establishing proctitis remission at Week 24, in subjects that had moderately to severely active proctitis at baseline
- To evaluate the safety and tolerability of filgotinib

CCI

3. STUDY DESIGN

3.1. Endpoints

The primary efficacy endpoint is:

- Proportion of subjects establishing combined fistula response at Week 24

The secondary efficacy endpoints are:

- Proportion of subjects establishing combined fistula remission at Week 24
- Time to clinical fistula response
- Time to clinical fistula remission
- Proportion of subjects achieving proctitis remission at Week 24, in subjects that had moderately to severely active proctitis at baseline

[figure not shown]
CCI

3.2. Study Design

This study is a Phase 2, double-blind, randomized, multicenter study evaluating the efficacy and safety of filgotinib versus placebo in the treatment of perianal fistulizing CD. A schematic of this study is provided in [Figure 3-1](#).

Figure 3-1. Study Design Schematic

FIL = filgotinib; PBO = placebo; mg = milligram.

* Non-responders (luminal disease) are defined as subjects who either had a baseline CDAI score ≥ 220 and never achieve a ≥ 70 -point CDAI reduction from baseline at any point up to and including Week 10 OR had a baseline CDAI score < 220 and have an increase in CDAI of ≥ 100 points from baseline, with CDAI ≥ 220 at Week 10.

Non-responders (perianal fistulizing disease) are defined as subjects who meet the following criteria for PDAI symptom subscores: "Discharge" subscore of >1 and ≥ 1 -point increase from baseline at Week 6 and Week 10 OR "Pain/restriction of activities" subscore of >1 and ≥ 1 -point increase from baseline at Week 6 and Week 10

** Disease worsening is defined as an increase in CDAI of ≥ 100 points from the Week 10 value with CDAI score ≥ 220 points at 2 consecutive visits

*** Subjects who are non-responders, meeting disease worsening criteria, or complete the study at Week 24, will have the option to enter a separate LTE study, if eligible.

This study includes:

- Screening (Day -30 to -1)
- Randomization
- Blinded Treatment Period (Day 1 to Week 24)

Efficacy assessment: At Week 24, physical examination, flexible sigmoidoscopy to assess presence of proctitis, and MRI to assess fistula response

Subjects who complete all procedures per protocol, including the MRI at Week 24, may be offered the option to continue into a separate Long Term Extension (LTE) study (GS-US-419-3896), if deemed appropriate by the investigator

- Subjects who are non-responders at Week 10 (see Section 3.6 OR Section 3.7) or who meet disease worsening criteria (see Section 3.8) after Week 10 will have the option to enter the LTE study, if eligible.
- Post Treatment (PTx) safety assessments:

All subjects completing this study will be offered the option to continue study drug in a blinded fashion in the LTE study, if eligible

Subjects who are eligible and opt to participate in the LTE study can continue into the LTE study without PTx safety assessments

Subjects who opt out of the LTE study will return to clinic 30 days after the last dose of study drug for PTx safety assessments

3.3. Study Treatments

Based on protocol eligibility criteria, subjects will be screened for enrollment and randomized into 1 of 3 treatment groups in a blinded fashion in a 2:2:1 ratio as follows:

Treatment group 1 (n = 30): filgotinib 200 mg and PTM filgotinib 100 mg, once daily

Treatment group 2 (n = 30): filgotinib 100 mg and PTM filgotinib 200 mg, once daily

Treatment group 3 (n = 15): PTM filgotinib 200 mg and PTM filgotinib 100 mg, once daily

Note: US males who are not dual refractory will be randomized in a 2:1 ratio to either filgotinib 100 mg or matching placebo. For the purposes of this protocol, US males who have failed at least one prior TNF antagonist AND either previously failed vedolizumab induction therapy or are concomitantly taking vedolizumab at Day 1 and present with actively draining perianal fistulae despite continued vedolizumab therapy will be considered as dual refractory patients. This assessment is based on recently published data from a subgroup analysis of the GEMINI-2 study, showing a beneficial effect of vedolizumab treatment for patients that were randomized with actively draining perianal fistulae at baseline (Feagan 2018).

Treatment assignments will be stratified according to the following factors:

- Anatomy of draining perianal fistulae at screening determined by MRI (simple *versus* complex)
- Receiving vedolizumab therapy concomitantly at Day 1 (Yes or No)
- Presence of moderately to severely active proctitis (Yes or No)

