### **3.2. Subject Grouping**

For analyses based on the All Randomized Analysis Set and the FAS, subjects will be grouped according to the treatment to which they were randomized. For analyses based on the Safety Analysis Set and Biomarker Analysis Set, subjects will be grouped according to the actual treatment received. The actual treatment received will differ from the randomized treatment only when their actual treatment differs from randomized treatment for the entire treatment duration.

CCI

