### **3.4. Examination of Subject Subgroups**

There are no prespecified subject subgroups for efficacy and safety analyses.

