## 4. SUBJECT DISPOSITION

### 4.1. Subject Enrollment and Disposition

A summary of subject enrollment will be provided by treatment group for each country, investigator within a country, and overall. The summary will present the number and percentage of subjects enrolled. For each column, the denominator for the percentage calculation will be the total number of subjects analyzed for that column.

A similar enrollment table will be provided by randomization stratum. The denominator for the percentage of subjects in the stratum will be the total number of enrolled subjects. If there are discrepancies in the value used for stratification assignment between the IWRS and the clinical database, the value collected in the clinical database will be used for the summary. A listing of subjects with discrepancies in the value used for stratification assignment between the IWRS and the clinical database at the time of data finalization will be provided.

The randomization schedule used for the study will be provided as an appendix to the CSR.

A summary of subject disposition will be provided by treatment group and overall. This summary will present the number of subjects screened, the number of subjects who met all eligibility criteria but were not randomized with reasons subjects were not randomized, the number of subjects randomized, and the number of subjects in each of the categories listed below:

- All Randomized Analysis Set
- Full Analysis Set
- Safety Analysis Set
- [REDACTED]
- [REDACTED]
- Completed study drug
- Continuing study drug (for analysis other than final analysis)
- Did not complete study drug with reasons for premature discontinuation of study drug
- Completed study
- Continuing study (for analysis other than final analysis)
- Did not complete the study with reasons for premature discontinuation of study

For the status of study drug and study completion and reasons for premature discontinuation, the number and percentage of subjects in each category will be provided. The denominator for the percentage calculation will be the total number of subjects in the Safety Analysis Set corresponding to that column.

The following by-subject listings will be provided by subject identification (ID) number in ascending order to support the above summary tables:

- Reasons for premature study drug or study discontinuation (A separate listing of reasons for premature study drug or study discontinuation due to COVID-19 will be created.)

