## 5. BASELINE CHARACTERISTICS

### 5.1. Demographics and Other Baseline Characteristics

Subject demographic variables and other baseline characteristics will be summarized by treatment group and overall using descriptive statistics for continuous variables, and using the number and percentage of subjects for categorical variables. The summary of demographic data will be provided for the Safety Analysis Set.

- Age (years, on the date of first dose of the study drug)
- Age group (< 65 years,  $\geq$  65 years)
- Sex at birth (female, male)
- Race
- Ethnicity (Hispanic or Latino, Not Hispanic or Latino)
- Geographic region (United States [US], non-US)
- Weight (in kg)
- Height (in cm)
- Body mass index (BMI; in kg/m^2)
- Smoking status (former, current, never)

A by-subject demographic listing, including the informed consent date, will be provided by subject ID number in ascending order.

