### **6.2.2. Analysis of the Primary Efficacy Endpoint**

The number and proportion of subjects establishing combined fistula response at Week 24 for each treatment group will be summarized with corresponding 90% exact CI by Clopper-Pearson method. The difference in proportions between each filgotinib dose group and the placebo group will be presented along with the associated 90% CI. No formal hypothesis testing will be performed.

For subjects who completed the Week 24 visit, the following missing value imputation will be used before deriving the proportion of subjects establishing combined fistula response at Week 24:

- If the clinical fistula assessment data is missing at Week 24, then the number of draining external perianal fistula openings at Week 24 will be imputed by Last Observation Carried Forward (LOCF) method using the number of draining external perianal fistulae openings from the last available scheduled or unscheduled visit, among draining external perianal fistulae openings at baseline only.
- If the MRI data is missing at Week 24, then absence of fluid collection > 1 cm will be imputed based on whether there was an absence of fluid collection > 1 cm at baseline (Yes, No), which will be derived from the size of fluid collections at baseline from the Total Fistula Score CRFs.

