### 6.3.2. Analysis of the Secondary Efficacy Endpoints

For binary endpoints, the same statistical analysis method for analyzing the primary efficacy endpoint will be utilized.

If the proctitis SES-CD score is missing at Week 24, no imputation will be done and the subject will be considered a non-responder when deriving the proportion of subjects achieving proctitis remission at Week 24.

For time-to-event secondary efficacy endpoints, the summary statistics (eg, median, Q1, Q3) from the Kaplan-Meier method will be provided for each treatment group. Plot of Kaplan-Meier curves will also be provided. The Cox proportional hazards model will be used to estimate the hazard ratio with the corresponding 90% CI. Subjects not known to have a clinical fistula response (or remission) will have their clinical fistula response (or remission) time censored at the last perianal fistula assessment date.

No formal hypothesis testing will be performed.

CCI

CCI

[figure not shown]
CCI

CCI

CCI

CCI

CCI

CCI

The figure consists of a 10x10 grid of black bars on a white background. The bars are arranged in a pattern where most are horizontal, with some vertical and diagonal variations. The bars are of varying lengths, creating a stepped effect. The grid is bounded by a thick black border.

CCI

CCI

■

■

■

■

■

■

■

■

■

■

■

■

■

■

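### The 200 mg versus placebo contrast uses placebo subjects from a two-arm allocation scheme who could not have been assigned 200 mg

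*Protocol*

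**What the plan says.** Protocol Section 3.3 and SAP Section 1.2 describe two allocation schemes. The general one is 2:2:1 to 200 mg, 100 mg and placebo. The exception is that "US males who are not dual refractory will be randomized in a 2:1 ratio to either filgotinib 100 mg or matching placebo". The listed stratification factors are fistula anatomy, active proctitis and concomitant vedolizumab (prior TNF antagonist exposure before amendment 4). The allocation scheme is not among them.

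The Full Analysis Set contains everyone randomised and dosed, and in it "subjects will be grouped according to the treatment to which they were randomized" (SAP Section 3.2). For the primary endpoint, "The difference in proportions between each filgotinib dose group and the placebo group will be presented along with the associated 90% CI" (SAP Section 6.2.2; Protocol Section 8.5.1 agrees). SAP Section 6.3.2 extends this: "For binary endpoints, the same statistical analysis method for analyzing the primary efficacy endpoint will be utilized". For the time-to-event endpoints, "The Cox proportional hazards model will be used to estimate the hazard ratio with the corresponding 90% CI". SAP Section 3.4 adds that "There are no prespecified subject subgroups for efficacy and safety analyses".

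No legible text limits the placebo comparator for 200 mg or adjusts for the allocation scheme. Parts of SAP Section 6 are redacted, but Section 6.2.2 is legible.

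**The concern.** A restricted US male has probability 0 of 200 mg, 2/3 of 100 mg and 1/3 of placebo. Everyone else has 2/5, 2/5 and 1/5. Restricted subjects therefore appear in the placebo and 100 mg groups but never in the 200 mg group.

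The 200 mg minus placebo difference is one of the two contrasts that serve the primary objective. As planned, it combines the treatment effect with any difference in placebo response between restricted subjects and the rest. The two kinds of subject could well differ, since the restricted ones are all male, all from the US and defined by biologic history. The planned interval makes no allowance for this. The tables by country, sex, region and prior biologic use could reveal an imbalance but would not remove it from the estimate.

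**Working it through.** **The plan's own figures.** 75 × (2, 2, 1)/5 gives 30/30/15, as in Protocol Section 8.8. The exact 90% limits in Table 8-1 also reproduce, for example 15/30: 33.9% to 66.1%, printed as 34% to 66%.

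**Two schemes together.** Let f be the share of all 75 subjects who are restricted. The documents do not give f, so it is varied.

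- n(200 mg) = 75(1−f) × 2/5
- n(100 mg) = 75(1−f) × 2/5 + 75f × 2/3
- n(placebo) = 75(1−f)/5 + 75f/3
- restricted share of placebo: s = (75f/3)/n(placebo)

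At f = 20%: 24, 34 and 17 subjects, with s = 5/17 = 29%. In the 100 mg group the restricted share is 10/34 = 29%, the same. This equality holds at every f because 100 mg to placebo is 2:1 in both schemes, so only the 200 mg contrast is exposed.

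**Shift.** Let the gap be the response rate of restricted minus eligible placebo subjects (assumed). The pooled placebo rate moves by s × gap, so the contrast moves by the same amount in the opposite direction.

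| f | 200/100/placebo | s | shift, 10-point gap | shift, 20-point gap |
|---|---|---|---|---|
| 10% | 27/32/16 | 16% | 1.6 | 3.1 |
| 20% | 24/34/17 | 29% | 2.9 | 5.9 |
| 30% | 21/36/18 | 42% | 4.2 | 8.3 |

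**Coverage.** Assumed: 200 mg response 40%, eligible placebo 20%, so the true difference is 20 points. The SAP does not name the method for the interval of the difference; Newcombe is assumed. Coverage comes from exact binomial enumeration, with placebo split (eligible + restricted) as 13+3, 12+5 and 10+8.

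| f | pooled, gap +10/−10 | pooled, gap +20/−20 | 2:2:1 subjects only |
|---|---|---|---|
| 10% | 89.7/90.7 | 88.6/90.5 | 89.8 |
| 20% | 89.1/89.9 | 86.9/88.5 | 89.3 |
| 30% | 86.7/89.6 | 81.2/86.3 | 89.7 |

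With an 11+7 split at f = 30%, the ±20 results are 82.9/87.6, against 90.8 restricted.

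**Precision cost.** Half-width = 1.645 × √(0.24/n(200 mg) + 0.16/n(control)). At f = 20%: √(0.24/24 + 0.16/17) gives 22.9 points pooled; √(0.24/24 + 0.16/12) gives 25.1 points restricted.

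| f | controls, pooled → restricted | half-width | RMSE restricted | RMSE pooled, gap +10/−10 | RMSE pooled, gap +20/−20 |
|---|---|---|---|---|---|
| 10% | 16 → 13.5 | 22.6 → 23.7 | 14.6 | 14.1/13.6 | 14.6/13.6 |
| 20% | 17 → 12 | 22.9 → 25.1 | 15.3 | 14.5/13.8 | 15.6/14.2 |
| 30% | 18 → 10.5 | 23.4 → 26.9 | 16.6 | 15.3/14.3 | 17.4/15.6 |

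Under these rates, restriction lowers RMSE only if restricted subjects respond better by more than roughly 20–22, 17.5 or 16.5 points at f = 10, 20 or 30%. Within the ±20-point range examined, it does not when they respond worse.

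**The case against.** The strongest reply is that the damage may be negligible and the cure often costs accuracy. At f = 0 nothing changes. At f = 10% with a 10-point gap, the shift is 1.6 points against a half-width of 22.6. A 20-point gap around an eligible placebo rate of 20% means that restricted subjects respond at 0% or 40%, and no text supports either. At a 10-point gap, Newcombe coverage hardly falls up to f = 20%, and the pooled estimate has the lower RMSE in every scenario. The coverage comparison also depends on the interval method: with Wald at f = 20%, pooled coverage at gap +20/0/−20 is 86.0/87.0/82.5 against 85.8 restricted, so it is clearly worse only at −20. All of this stands. It rules out any claim that restriction is more accurate in general, and it is why the pooled result should be kept.

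It does not remove the structural point. Part of the 200 mg control group was never randomised against 200 mg, and no increase in sample size would correct the resulting shift. The stratified Cox model in Protocol Section 8.5.2 would not help either, because the listed strata omit the allocation scheme; SAP Section 6.3.2 does not mention stratification.

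Three stronger readings are tempting but unsupported:

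- A reader might infer that the 200 mg comparison is not randomised. Every subject is randomised; the fault is that controls from a second scheme are pooled in.
- A reader might infer a bias for or against filgotinib. The documents give no response rates by scheme, so no direction can be stated.
- A reader might infer that the 30/30/15 sizes are wrong. The total is called approximate and the interim counts estimated, so that is at most editorial.

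**Conclusion.** The point holds as a matter of structure: the 200 mg contrast is not like for like, and the 100 mg contrast is. Its size is unknown. Under assumed shares of 10 to 30% and gaps of 10 to 20 points, the shift is 1.6 to 8.3 points in either direction. Coverage loss is negligible unless both the share and the gap are large; the lowest Newcombe value found is 81.2%, at f = 30% with a gap of +20.

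A reader might go on to infer a false-positive risk. The documents do not support that, because no formal hypothesis test is planned. The consequence is a possibly biased estimate and interval in a descriptive trial. This is an inexpensive improvement to the analysis plan, not a flaw that invalidates the trial.

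**What to change.** In SAP Sections 6.2.2 and 6.3.2, state before the blind is broken that the 200 mg versus placebo difference in proportions and hazard ratio are estimated in subjects randomised under the 2:2:1 scheme, and report the pooled-placebo contrast beside them. Keep all subjects for 100 mg versus placebo. Define the flag by the scheme actually applied at randomisation. SAP Section 4.1 says that "The randomization schedule used for the study will be provided as an appendix to the CSR", but no text says that the scheme is stored as a variable, so it may have to be derived from the randomisation records. Name the method for the interval of the difference.

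No new patients are needed. The price is the loss of controls and the wider interval shown above (about 1.1, 2.2 or 3.5 points in half-width), and often a higher RMSE. What it buys is a like-for-like randomised comparison.

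Separately, the Protocol describes in different ways which US males may be allocated 200 mg. Section 1.5 refers to failure of at least two biologics, TNF antagonists or vedolizumab. The synopsis definition of dual refractory mentions TNF antagonist failure with concomitant vedolizumab. Section 3.3 adds previously failed vedolizumab induction. A man who failed two TNF antagonists and never had vedolizumab meets the Section 1.5 wording but is not dual refractory under Section 3.3. These texts decide who falls under which scheme and must be reconciled; no view is taken on which is right.

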3.4. Duration of Treatment

Randomized subjects will receive a maximum of 24 weeks of study drug. Subjects who are non-responders based on the results of the Week 10 assessments (see Section 3.6 OR Section 3.7 or meeting disease worsening criteria after Week 10 (see Section 3.8) must be discontinued from blinded treatment (see Section 3.5.2).

3.5. Criteria for Study Drug Interruption or Discontinuation

3.5.1. Study Drug Interruption Considerations

The Study Medical Monitor should be consulted prior to study drug interruption when medically feasible.

Study drug interruption should be considered in the following circumstances (*prior to resumption of study drug, the investigator should discuss the case with the Study Medical Monitor*):

- Intercurrent illness that would, in the judgment of the investigator, affect assessments of clinical status to a significant degree
- Subject is scheduled for elective or emergency surgery (excluding minor skin procedures under local or no anesthesia); timing of study drug interruption should be determined in consultation with the Study Medical Monitor
- Any subject who develops a new infection during the study should undergo prompt and complete diagnostic testing appropriate for an immunocompromised individual, and the subject should be closely monitored

NOTE: During the time of study drug interruption for any of the above, the subject may continue to have study visits and to take part in procedures and assessments, if deemed medically appropriate by the investigator.

3.5.2. Study Drug Discontinuation Considerations

The Study Medical Monitor should be consulted prior to study drug discontinuation when medically feasible.

Study drug must be permanently discontinued in the following instances:

- Any opportunistic infection
- Any **serious** infection that requires antimicrobial therapy or hospitalization, or any infection that meets SAE reporting criteria.
- Febrile neutropenia (temperature $> 38.3^{\circ}\text{C}$ or a sustained temperature of $> 38^{\circ}\text{C}$ for more than one hour) with absolute neutrophil count of $< 1,000/\text{mm}^3$

- Symptomatic anemia (eg, signs/symptoms including pallor, shortness of breath, new heart murmur, palpitations, lethargy, fatigue) with hemoglobin < 7.5 g/dL, or if transfusion is indicated regardless of hemoglobin value
- Complicated herpes zoster infection (with multi-dermatomal, disseminated, ophthalmic, or CNS involvement)
- Evidence of active Hepatitis C Virus (HCV) during the study, as evidenced by HCV RNA positivity
- Evidence of active Hepatitis B Virus (HBV) during the study, as evidenced by HBV DNA positivity
- Any thromboembolic event that meets SAE reporting criteria
- Unacceptable toxicity, or toxicity that, in the judgment of the investigator, compromises the subject's ability to continue study-specific procedures or is considered to not be in the subject's best interest
- Subject request to discontinue for any reason
- Subject noncompliance
- Pregnancy during the study; refer to Section [7.7.2.1](#)
- Discontinuation of the study at the request of Gilead, a regulatory agency or an institutional review board or independent ethics committee (IRB/IEC)
- Subject use of prohibited concurrent therapy may trigger study drug discontinuation; consultation should be made with the Study Medical Monitor.
- Laboratory Criteria: After becoming aware of any of the below described abnormal laboratory changes occurring at any one time, an unscheduled visit (ie, sequential visit) should occur to retest within 3 to 7 days (except creatinine, which should be retested 7 to 14 days apart).
 - Two sequential neutrophil counts < 750 neutrophils/mm³ (SI: < 0.75x10⁹ cells/L)
 - Two sequential platelet counts < 75,000 platelets/mm³ (SI: < 75.0x10⁹ cells/L)

Two sequential aspartate aminotransferase (AST) or alanine aminotransferase (ALT) elevations > 3 times the upper limit of normal range (x ULN) and at least one of the following confirmed values:

- total bilirubin > 2 x ULN
- INR > 1.5
- or accompanied by symptoms consistent with hepatic injury

For any subject with an initial AST or ALT elevation > 3 x ULN, at the time of the second confirmatory draw, an INR, prothrombin time (PT), and partial thromboplastin time (PTT) must also be drawn.

Two sequential AST or ALT > 5 x ULN

Two sequential values for estimated creatinine clearance (CL_{cr}) < 35 mL/min based on the Cockcroft-Gault (CC&G) formula

$$\text{Male: } \frac{(140 - \text{age in years}) \times (\text{wt in kg})}{72 \times (\text{serum creatinine in mg/dL})} \text{ } CL_{cr} \text{ (mL/min)}$$

$$\text{Female: } \frac{(140 - \text{age in years}) \times (\text{wt in kg}) \times 0.85}{72 \times (\text{serum creatinine in mg/dL})} \text{ } CL_{cr} \text{ (mL/min)}$$

Subjects are free to withdraw from the study at any time without providing reason(s) for withdrawal and without prejudice to further treatment. The reason(s) for withdrawal will be documented in the electronic case report form (eCRF).

Subjects who permanently discontinue study drug for any reason should discuss their continued care plan with their physician.

Subjects who permanently discontinue study drug for pregnancy should not continue in the study; if there are any questions regarding permanent discontinuation, these should be discussed with the Sponsor.

Subjects withdrawing from the study should complete Early Termination (ET), followed by PTx assessments 30 days after the last dose of study drug (Refer to Section 6.13 for Post Treatment assessments).

Reasonable efforts will be made to contact subjects who are lost to follow-up. All contacts and contact attempts must be documented in the subject's file.

The Sponsor has the right to terminate the study at any time in case of safety concerns or if special circumstances concerning the study medication or the company itself occur, making further treatment of subjects impossible. In this event, the investigator(s) and relevant authorities will be informed of the reason for study termination.

